10.1.2. Immunogenicity endpoints

The primary laboratory endpoint is an assessment of the immunogenicity of the two regimens. Serum antibodies (such as Anti-MAGE-A3) seropositivity status (a seropositive patient is a patient whose titre is greater than or equal to the cut-off value) will be the primary immune endpoints assessed. Seropositivity will be assessed at baseline, after 2, 4, 6, 7 and 9 administrations, post-treatment (i.e., at concluding visit) and one year after concluding visit (i.e., at follow-up visit 2). Cellular immune assays will also be determined as a secondary endpoint. For methods of analysis, see Section 10.7.4.

Refer to Section 10.3 for details on the statistical analyses.

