- Treatment groups: Two groups, recMAGE-A3 + AS15 ASCI and recMAGE-A3 + AS15 ASCI in combination with Poly IC:LC.
- Treatment schedule: The study treatment will consist of an Induction phase and a Maintenance phase. During the Induction phase, recMAGE-A3 + AS15 ASCI +/- Poly IC:LC will be administered 5 times at 3-week intervals. During the Maintenance phase, recMAGE-A3 + AS15 ASCI +/- Poly IC:LC will be administered 8 times at 3-month intervals. A total of 13 doses of recMAGE-A3 + AS15 ASCI +/- Poly IC:LC will be administered over a period of 27 months.
- Control: recMAGE-A3 + AS15 ASCI.
- Data collection: Case report form (CRF).
- Duration of the study: The total duration of the study treatment phase (including concluding visit) is 30 months per patient. The duration of active follow-up for survival, recurrence and serious adverse events (SAEs) related to the study participation will be 5 years from the first administration of study treatment.

Main inclusion criteria:

- Patients with histologically proven resected stage IV cutaneous or mucosal melanoma rendered free of disease.
- The patient's tumor expresses MAGE-A3, as determined by RT-PCR analysis on formalin-fixed paraffin-embedded (FFPE) tumor tissue sample obtained during the screening phase.
- ECOG performance status 0 or 1.
- Adequate bone marrow reserve with Hg >10, platelets > 100,000, and WBC >3000 per mm³.

Number of patients:

The study will enroll up to 44 patients to end up with 40 evaluable patients in two cohorts of 20 patients each.

Endpoints:

Primary endpoints:

- Toxicity and tolerability in the two study arms (recMAGE-A3 + AS15 ASCI and recMAGE-A3 + AS15 ASCI in combination with Poly IC:LC) defined by the adverse events and serious adverse events.
- Immunogenicity in the two study arms (recMAGE-A3 + AS15 ASCI and recMAGE-A3 + AS15 ASCI in combination with Poly IC:LC) defined by antibodies serum titer (such as anti-MAGE-A3).

Secondary endpoints:

- Immunogenicity as measured by T cell responses directed against MAGE-A3 antigen.
- Relapse-Free Survival (RFS), defined as the time from randomization to the date of first relapse of melanoma or of death, whichever comes first.
- Overall Survival (OS), defined as the time from randomization to the date of death.
- A potential correlation between gene expression profile and treatment clinical activity (RFS) in both study arms (recMAGE-A3 + AS15 ASCI and recMAGE-A3 + AS15 ASCI in combination with Poly IC:LC).

TABLE OF CONTENTS	PAGE

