2. OBJECTIVES

2.1. Primary objectives

The primary objectives of this clinical trial are:

- To evaluate the safety and tolerability of recMAGE-A3 + AS15 ASCI compared to recMAGE-A3 + AS15 ASCI in combination with Poly IC:LC in patients with resected stage IV melanoma.
- To evaluate the immunogenicity of recMAGE-A3 + AS15 ASCI compared to recMAGE-A3 + AS15 ASCI in combination with Poly IC:LC as measured by antibodies serum titers (such as anti-MAGE-A3) in patients with resected stage IV melanoma.

Refer to Section 10.1 for the definition of the primary endpoints.

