The sample size for this trial is calculated based on the primary immune endpoint of a serologic response to treatment. In a GSK trial using recMAGE-A3 + AS15 ASCI in a similar patient population, the total anti-MAGE-A3 IgG antibody measured at approximately 6 months at the first vaccine of the maintenance phase for the ASCI arm without Poly IC:LC had a geometric mean of about 7,000 and a standard deviation of no more than 0.28 on the log scale. It is anticipated that the ASCI arm with Poly IC:LC will further increase such anti-MAGE-A3 IgG antibody measurement at 6 months to about 10,500 for a 50% enhancement of the effect. Therefore, 20 patients per arm will yield 62% power for such detection of the anti-MAGE-A3 IgG antibody difference between the two arms at a one-sided significance level of 0.05. Power calculations for this trial will be only for the immune primary endpoint, since little toxicity is expected from either of the treatment arms on which to base a power calculation. Table 1 lists the change in power if the standard deviation deviates from the assumed value of 0.28 when everything else is the same. We plan to enroll 20 patients per arm for a total of 40 patients. To account for an approximate 10% loss-to-follow-up rate in this study, up to 44 patients may be enrolled.

The change in power if the standard deviation deviates from the assumed value of 0.28:

Standard Deviation	0.28	0.26	0.24	0.22	0.20
Power	0.62	0.68	0.74	0.80	0.86

A median RFS of about 8 months was observed for similar patients treated without adjuvant therapy. A median RFS of 12 months is expected of patients treated with recMAGE-A3 + AS15 ASCI alone in resected stage IV melanoma. Adding Poly IC:LC to this ASCI regimen might double the median RFS to 24 months. The power calculation shows that 20 patients per arm would have a power of about 61% for detecting such difference in RFS between the two arms with a one-sided type error rate of 0.05, assuming an accrual rate of 2.5 patients per month and a 3-year follow-up after the completion of accrual.

Assuming an accrual rate of 2.5 patients per month, it would take up to 18 months to enroll 44 patients to this trial.

Data Analyses Plan

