Demographic and disease characteristics as well as other baseline variables for all patients randomized will be tabulated and analyzed using the standard descriptive statistics such as frequency and percentage tables for discrete variables and mean, median, SD, range, and interquartiles for continuous variables. These data will be reported by arm and may be further stratified by subgroups, e.g., those patients with favorable/unfavorable gene signature, of interest.

The total anti-MAGE-A3 IgG antibody measured at various time points over the course of treatment will be descriptively reported by arm with the usual summary statistics as well as with plots and confidence intervals (CIs) to discern any time change pattern of interest. Comparisons between the two arms will be on the log scale using the two sample t test. If the normal distribution assumption is violated for log (total anti-MAGE-A3 IgG antibody), then non-parametric Wilcoxon test and/or other transformations such as ln and square root will be considered as well.

In order to determine whether recMAGE-A3 + AS15 ASCI +/- poly IC:LC is able to induce a specific T-cell response to the MAGE-A3 protein and to evaluate the T-cell response in both treatment groups, the percentage of T-cells simultaneously producing IFN γ and IFN α will be assessed after 5, and after 9 recMAGE-A3 + AS15 ASCI +/- poly IC:LC injections.

The cutoff value for a positive response is defined as 2 standard deviations over the mean percentage of double positive events in control wells. Anti-MAGE-A3 T-cell response is considered as positive when there are at least 3 more positive wells at any point after immunization than at baseline. This variable will be reported using both point estimates and 95% CIs for various subgroups of patients, e.g., arms or patients with favorable/unfavorable gene signature. Antibodies (such as Anti-MAGE-A3) seropositivity status, defined for a patient whose anti-body titer is greater or equal to the cutoff value, will be analyzed similarly.

RFS and OS will be analyzed using the Kaplan-Meier product-limit method as well as the Cox proportional hazards regression models. The Log-rank test for comparing RFS between the two arms will be performed and reported. Confidence interval for the median and survival rates at different time points will be constructed if needed.

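### Section 10.1.2 makes seropositivity the primary immune endpoint, but the trial is powered and tested on log antibody titre, and no sampled visit is named for the comparison

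*Combined protocol and SAP*

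**What the plan says.** **Titre as the endpoint.** The synopsis lists immunogenicity in the two arms as a primary endpoint, "defined by antibodies serum titer (such as anti-MAGE-A3"). The objective in section 2.1 also speaks of serum titres.

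**Seropositivity as the endpoint.** Section 2.1 then adds: "Refer to Section 10.1 for the definition of the primary endpoints". Section 10.1.2 gives that definition as seropositivity status (a seropositive patient being one "whose titre is greater than or equal to the cut-off value) will be the primary immune endpoints assessed". It lists eight assessment times and ends: "Refer to Section 10.3 for details on the statistical analyses".

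**What section 10.3 powers.** It calls the sizing endpoint a serologic response, but the inputs are continuous. They are control-arm total IgG "measured at approximately 6 months at the first vaccine of the maintenance phase", with geometric mean about 7,000 and SD at most 0.28 on the log scale, against about 10,500 with Poly IC:LC. It concludes: "Therefore, 20 patients per arm will yield 62% power for such detection of the anti-MAGE-A3 IgG antibody difference between the two arms", at one-sided 0.05.

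**What section 10.3 tests.** For titre: "Comparisons between the two arms will be on the log scale using the two sample t test", with Wilcoxon or another transformation as fallback. The T-cell response gets point estimates and 95% CIs, and seropositivity, for a patient "whose anti-body titer is greater or equal to the cutoff value, will be analyzed similarly".

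**Section 10.7.4** lists geometric mean titre, seropositivity and antibody response side by side and ranks none of them. Section 10.4.3 rules out any multiplicity adjustment.

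**The concern.** Followed literally, the document makes primary a binary variable that has no between-arm test and to which the quoted power does not apply. Around the planning time point, that variable could hardly show the effect the trial was designed to find. A 50% rise in titre among patients already far above an assay cut-off leaves the proportion above it almost unchanged.

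The time point is also open. The power calculation refers to about 6 months, but the t test is not tied to any visit. In an open-label trial with no multiplicity adjustment, two candidate variables and several sampled visits leave room to decide after the fact which result answers whether Poly IC:LC improved immunogenicity.

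**Working it through.** **1. Reproduce the plan's power.** Inputs from section 10.3: 20 per arm, geometric means 7,000 and 10,500, SD 0.28, one-sided alpha 0.05. The base of the logarithm is not stated.

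On log10, the difference is log10(10,500/7,000) = log10(1.5) = 0.1761. The noncentrality is 0.1761 / (0.28 × √(2/20)) = 0.1761 / 0.0885 = 1.99, with 38 degrees of freedom and critical t 1.686. Power from the noncentral t distribution:

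| SD | Plan | Recomputed |
|---|---|---|
| 0.28 | 0.62 | 0.621 |
| 0.26 | 0.68 | 0.677 |
| 0.24 | 0.74 | 0.737 |
| 0.22 | 0.80 | 0.800 |
| 0.20 | 0.86 | 0.862 |

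On the natural log, ln(1.5) = 0.4055 with SD 0.28 gives 99.8%. The plan's table is therefore a calculation for log10 titre.

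**2. Seropositivity under the same planning values.** I assume log-normal titres. Sections 6.4.6 and 10.6.2 give no numerical cut-off c, so I use a range. The proportion positive is Φ((log10 GMT − log10 c) / 0.28). For controls at c = 2,000 this is Φ(log10(3.5)/0.28) = Φ(1.943) = 0.974. The plan names no test, so power is for an assumed one-sided Fisher test at 0.05, by exact enumeration over 20 + 20 patients.

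| Cut-off | Control positive | Combination positive | Power |
|---|---|---|---|
| 1,000 | 99.9% | 99.99% | about 0 |
| 2,000 | 97.4% | 99.5% | 0.01% |
| 3,000 | 90.6% | 97.4% | 2.3% |
| 3,500 | 85.9% | 95.6% | 7.7% |
| 5,000 | 69.9% | 87.5% | 26% |
| 7,000 | 50.0% | 73.5% | 33% |
| 8,500 | 38.2% | 62.8% | 32% |

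The control rate stays at or above 99% up to a cut-off of about 1,560 (10^(log10 7,000 − 2.326 × 0.28)).

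**3. A check that needs no cut-off.** Suppose all 20 combination patients are positive. With k negative controls, the one-sided Fisher p is C(20,k)/C(40,k). For k = 4 it is 4,845/91,390 = 0.053; for k = 5 it is 15,504/658,008 = 0.024. At least five of 20 controls must be seronegative. That has probability 0.3% if controls are 95% positive, 4.3% if 90%, and 17% if 85%.

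**4. The visit.** Six months, the first maintenance dose, is Visit 6 (week 24). Tables 5, 6 and 8 and section 6.3.8 schedule humoral samples at Visit 5 (week 12) and Visit 7 (week 36), but none at Visit 6. Neither titre nor seropositivity is measured at the powered time point.

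**The case against.** The strongest defence is that only one antibody comparison is planned: log titre by t test, the variable used for the sample size and named in the synopsis and section 2.1. Section 10.1.2 itself points to 10.3. A proportion with no test attached is a weak rival, and the inputs to the 62% cannot describe a binary variable. This stands in part. The titre comparison is pre-specified, and the power figure can be traced to it. But the section that 2.1 designates as the definition names another variable, 10.7.4 ranks none, and the t test has no visit.

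A second objection is that the ceiling depends on an unstated cut-off. Section 1.2.3.3 says all patients in the earlier melanoma trial developed an antibody response, but in unresected disease, with two adjuvant systems pooled and no assay cut-off or time point. That is fair. Near-100% seropositivity is an inference about the period around 6 months; it is not shown after only two doses or one year after the concluding visit. The higher cut-offs in the table show that power could exceed a few percent, but none of those tried gives more than 33%. The conflict, the missing test and the missing power calculation do not depend on the cut-off.

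A third is that the sponsor could keep seropositivity as primary. It could, but would then have to state a cut-off, a between-arm test and its power.

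**Conclusion.** The concern holds and should be fixed. The primary immune endpoint is defined in two ways. The 62% power is correct for log10 titre under the 6-month planning values and does not apply to the seropositivity endpoint that 10.1.2 calls primary. Seropositivity has no planned between-arm test and no power calculation. Under log-normal titres with the plan's means and SD, its power in an assumed one-sided Fisher test runs from essentially zero at cut-offs up to 1,000 to about 33% at 7,000. Confidence is high on the mismatch. The ceiling is probable, and limited to the period around 6 months.

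**What to change.** Rewrite section 10.1.2 along these lines: the primary immune endpoint is log10 total anti-MAGE-A3 IgG titre at [one named visit with a scheduled humoral sample], compared between arms as in 10.3; seropositivity and antibody-response rates are descriptive secondary endpoints, reported by arm at each sampled visit.

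- **Visit.** Visits 5 and 7 are the sampled visits on either side of Visit 6. Make the choice in a dated decision, without knowledge of titres by arm, and record who had access to them.
- **Power.** State that the 62% assumes the 6-month geometric means and SD carry over to that visit, since the documents give none for Visit 5 or 7. Show the sensitivity: with the same difference, power is 47% at SD 0.35 and 39% at SD 0.40 (illustrative values above the plan's stated maximum of 0.28). State that the scale is log10.
- **Consistency.** Align the synopsis, 2.1, 10.1.2, 10.3 (including its serologic-response label), 10.6.2 and 10.7.4.

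The cost is a text amendment, the documented visit choice and a restated power assumption. No new samples or assays are needed. Section 6.4.2 ends immunology sampling on October 1, 2015 and allows analysis of existing samples to continue. If recruitment finished by February 2013 as Appendix A expects, the week-12 and week-36 samples were due by about the end of 2013.

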10.2. Secondary endpoints

10.2.1. Secondary clinical activity endpoints

Relapse-Free Survival (RFS), defined as the time from randomization to either the date of first recurrence of the disease or the date of death (whatever the cause), whichever occurs first.

Therefore, any death occurring without prior documentation of tumor relapse will be considered as an event (and will not be censored in the statistical analysis) as this approach is less prone to introduce bias. If no event has occurred by the time of the analysis, then the time to event will be censored at the date of the last assessment of the patient in question.

Any new primary cancer at another site, including second primary melanoma, will not be considered as a relapse and should be reported as a SAE.

Overall Survival (OS) defined as the interval from randomization to the date of death, irrespective of the cause of death; patients still alive will be censored at the date of the last assessment.

10.3. Study design/sample size and power/data analyses

Study Design

This is a 1:1 randomized, two-arm, open-label, Phase II, single-center study to evaluate the safety, tolerability and immunogenicity of recMAGE-A3 + AS15 ASCI with Poly IC:LC as adjuvant therapy compared to recMAGE-A3 + AS15 ASCI alone in MAGE-A3 positive patients with completely resected stage IV melanoma. Secondary objectives include: to describe the efficacy in terms of Relapse-Free Survival (RFS) and Overall Survival (OS) of the two arms; to collect preliminary data on the T cell immune response to the ASCI in the overall study population as well as subsets of patients of interest (e.g., arms and gene signature groups), and to evaluate the gene signature in all patients when possible. The study treatment will consist of an induction phase and a maintenance phase. During the induction phase, immunization with or

without Poly IC:LC will be administered 5 times at 3-week intervals. During the maintenance phase, immunization with recMAGE-A3 + AS15 with or without Poly IC:LC will be administered 8 times at 3-month intervals. The 13 immunizations with or without Poly IC:LC will be administered over a period of 27 months. The total duration of the study treatment phase (including concluding visit) is 30 months per patient. The duration of active follow-up for survival, recurrence and serious adverse events (SAEs) related to the study participation and concurrent GSK medications will be 5 years from the first administration of study treatment.

Sample Size/Power Calculations and Accrual

The sample size for this trial is calculated based on the primary immune endpoint of a serologic response to treatment. In a GSK trial using recMAGE-A3 + AS15 ASCI in a similar patient population, the total anti-MAGE-A3 IgG antibody measured at approximately 6 months at the first vaccine of the maintenance phase for the ASCI arm without Poly IC:LC had a geometric mean of about 7,000 and a standard deviation of no more than 0.28 on the log scale. It is anticipated that the ASCI arm with Poly IC:LC will further increase such anti-MAGE-A3 IgG antibody measurement at 6 months to about 10,500 for a 50% enhancement of the effect. Therefore, 20 patients per arm will yield 62% power for such detection of the anti-MAGE-A3 IgG antibody difference between the two arms at a one-sided significance level of 0.05. Power calculations for this trial will be only for the immune primary endpoint, since little toxicity is expected from either of the treatment arms on which to base a power calculation. Table 1 lists the change in power if the standard deviation deviates from the assumed value of 0.28 when everything else is the same. We plan to enroll 20 patients per arm for a total of 40 patients. To account for an approximate 10% loss-to-follow-up rate in this study, up to 44 patients may be enrolled.

The change in power if the standard deviation deviates from the assumed value of 0.28:

Standard Deviation	0.28	0.26	0.24	0.22	0.20
Power	0.62	0.68	0.74	0.80	0.86

A median RFS of about 8 months was observed for similar patients treated without adjuvant therapy. A median RFS of 12 months is expected of patients treated with recMAGE-A3 + AS15 ASCI alone in resected stage IV melanoma. Adding Poly IC:LC to this ASCI regimen might double the median RFS to 24 months. The power calculation shows that 20 patients per arm would have a power of about 61% for detecting such difference in RFS between the two arms with a one-sided type error rate of 0.05, assuming an accrual rate of 2.5 patients per month and a 3-year follow-up after the completion of accrual.

Assuming an accrual rate of 2.5 patients per month, it would take up to 18 months to enroll 44 patients to this trial.

Data Analyses Plan

Demographic and disease characteristics as well as other baseline variables for all patients randomized will be tabulated and analyzed using the standard descriptive statistics such as frequency and percentage tables for discrete variables and mean, median, SD, range, and interquartiles for continuous variables. These data will be reported by arm and may be further stratified by subgroups, e.g., those patients with favorable/unfavorable gene signature, of interest.

The total anti-MAGE-A3 IgG antibody measured at various time points over the course of treatment will be descriptively reported by arm with the usual summary statistics as well as with plots and confidence intervals (CIs) to discern any time change pattern of interest. Comparisons between the two arms will be on the log scale using the two sample t test. If the normal distribution assumption is violated for log (total anti-MAGE-A3 IgG antibody), then non-parametric Wilcoxon test and/or other transformations such as ln and square root will be considered as well.

In order to determine whether recMAGE-A3 + AS15 ASCI +/- poly IC:LC is able to induce a specific T-cell response to the MAGE-A3 protein and to evaluate the T-cell response in both treatment groups, the percentage of T-cells simultaneously producing IFN γ and IFN α will be assessed after 5, and after 9 recMAGE-A3 + AS15 ASCI +/- poly IC:LC injections.

The cutoff value for a positive response is defined as 2 standard deviations over the mean percentage of double positive events in control wells. Anti-MAGE-A3 T-cell response is considered as positive when there are at least 3 more positive wells at any point after immunization than at baseline. This variable will be reported using both point estimates and 95% CIs for various subgroups of patients, e.g., arms or patients with favorable/unfavorable gene signature. Antibodies (such as Anti-MAGE-A3) seropositivity status, defined for a patient whose anti-body titer is greater or equal to the cutoff value, will be analyzed similarly.

RFS and OS will be analyzed using the Kaplan-Meier product-limit method as well as the Cox proportional hazards regression models. The Log-rank test for comparing RFS between the two arms will be performed and reported. Confidence interval for the median and survival rates at different time points will be constructed if needed.

The descriptions and grading scales found in the CTEP Active Version of the NCI Common Terminology Criteria for Adverse Events (CTCAE v.4) will be utilized for AE reporting. The CTEP Active Version of the CTCAE is identified and located on the CTEP website at: http://ctep.cancer.gov/protocolDevelopment/electronic_applications/ctc.htm. All appropriate treatment areas should have access to a copy of the CTEP Active Version of CTCAE. Toxicity data will be summarized using the usual toxicity table by category and worst grade for the two ASCI regimens.

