6.3.8. Visits 6-13: Three-monthly maintenance treatment administrations

These visits will take place at 3-month intervals, i.e., at time-points 6, 9, ..., 27 months after Visit 1, with a permitted deviation from the scheduled time-point of up to 14 calendar days.

The following procedures will be performed at each of these visits:

- Physical examination (as at Visit 1, including ECOG performance status and disease assessment).
- A CT scan of the neck, chest and upper abdomen and pelvic CT scan.
- Before administration of study treatment the criteria for permanent stopping or postponement of study treatment (Sections 5.2.1.1 and 5.2.1.2) will be checked; if any of these is met, the patient will either be withdrawn from study treatment or the administration of study treatment will be postponed.
- Recording of (serious) adverse events and pIMD.
- A pregnancy test for females of childbearing potential.
- Recording of concomitant medications.
- Administration of the study treatment.

The following procedures will be performed before the administration of study treatment at Visits 7, 8 and 10:

- Blood samples (10 ml, as described in Section 6.4.2) for humoral immunity assays will be taken.

The following procedures will be performed once every year after Visit 1 (i.e. at Visits 8 and 12):

- Blood sampling (15 ml as described in Section 6.4.2) for haematological and chemical safety assays.

If any of the sixth to twelfth study treatment administrations had to be postponed (refer to Section 5.2.1.1 for criteria for postponement of study treatment), the subsequent Visit should be planned as close as possible to the 3-monthly interval of the original schedule, but with a minimum of 14 days between any two treatment administrations.

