6.4.2. Laboratory assays and immunological read-outs

Please refer to the GSK recommendations for details of biospecimen management (handling, storage and shipment) for specimens shipped to GSK Bio or contracted lab.

Samples will not be labeled with information that directly identifies the patients but will be coded with the identification number for the patient (patient number or requisition number).

Collected samples may be used for purposes related to the quality assurance of the laboratory tests described in this protocol. This may include the management of the quality of these current tests, the maintenance or improvement of these current tests, the development of new test methods for the markers described in this protocol, as well as making sure that new tests are comparable to previous methods and work reliably.

Table 8 specifies the laboratory assays and immunological read-outs that must be performed.

CONFIDENTIAL

Assay type	Test	Sample type	Laboratory	Timing
MAGE-A3 screening (mandatory)				
	MAGE-A3 expression testing on the tissue removed during resection	FFPE tumor tissue	GSK Bio or contracted lab	During screening
MAGE-A3 (optional)				
	If tissue from multiple lesions (e.g. primary tumor, lymph node, etc) are also available, this may be tested to examine whether they all express MAGE-A3	FFPE tumor tissue	GSK Bio or contracted lab	During study
Laboratory assays (mandatory)				
	Haematology	Blood (15 ml)	Moffitt CC laboratory	See Section 6.3
	White blood cell count			
	Neutrophils			
	Platelets			
	Lymphocytes			
	Haemoglobin			
	Biochemical values			
	LDH			
	Renal function			
	Creatinine			
	Hepatic function			
	Serum bilirubin			
	Aspartate transaminase (ASAT)			
	Alanine transaminase (ALAT)			
	Alkaline phosphatase			
Humoral Immunological read-outs (mandatory)				
	Humoral response (serum antibodies titers)	Blood (2 x 5 ml)	GSK or contracted lab	V1- wk 0 V3- wk 6 V5- wk 12 V7- wk 36 V8- wk 48 V10- wk 72 V14 (CV)-wk 120 F2- CV + 12m
Translational research (optional)				
	MAGE-A3 expression testing on relapse or new lesions	FFPE tumor tissue	GSK or contracted lab	In case of confirmed recurrence. Section 7.1
	Gene profiling			
	Gene profiling of resected lesions	Fresh tumor tissue stored in RNA later ^a	GSK or contracted lab	Screening Samples. Section 7.3
	Gene profiling of new lesions	Fresh tumor tissue stored in RNA later ^a	GSK or contracted lab	In case of confirmed recurrence. Section 7.4
	Serum analysis			

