10.7.4. Analysis of immunogenicity

The analysis of immunogenicity will be performed on the ATP population, cf. Section 10.4.3.

The immunogenicity induced by the recMAGE-A3 + AS15 +/- poly IC:LC ASCI will be assessed through calculation of the geometric mean titres (with 95% CI), the proportion of seropositive patients and antibody response in the two treatment groups. This will be done for antibodies at baseline, after 2, 4, 6, 7, and 9 dose administrations and post-treatment (i.e., at the concluding examination at Visit 14, 3 months after the injection of dose 13, cf. Section 6.3).

Antibody titres may also be investigated using reverse cumulative curves.

A possible correlation between the immunological response (such as antibody response to MAGE-A3) and RFS may be explored using a time-dependent Cox model.

The immunogenicity will also be evaluated in the gene signature-positive and gene signature negative populations, separately.

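### The 62% power is for the anti-MAGE-A3 titre at month 6 (Visit 6), where no humoral sample is scheduled; no sampled visit is named primary, and sections disagree on titre versus seropositivity

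*Combined protocol and SAP*

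**What the plan says.** Section 10.3 bases the sample size on total anti-MAGE-A3 IgG at about 6 months, at the first maintenance dose. The control geometric mean is about 7,000 and the log-scale SD at most 0.28. Poly IC:LC is expected to "increase such anti-MAGE-A3 IgG antibody measurement at 6 months to about 10,500 for a 50% enhancement of the effect". With 20 per arm and one-sided 0.05, the stated power is 62%.

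The humoral sampling schedule is given in several places:

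- Table 8 (Section 6.4.2) lists "V1- wk 0 V3- wk 6 V5- wk 12 V7- wk 36 V8- wk 48 V10- wk 72", then Visit 14 at week 120 and F2 one year later.
- Section 6.3.8 introduces the maintenance-phase humoral sample with "The following procedures will be performed before the administration of study treatment at Visits 7, 8 and 10".
- Section 10.7.4 says "This will be done for antibodies at baseline, after 2, 4, 6, 7, and 9 dose administrations and post-treatment".
- Tables 5, 6 and 7 agree: Visits 1, 3 and 5; Visits 7, 8, 10 and 14; F2.

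On the test, Section 10.3 says "Comparisons between the two arms will be on the log scale using the two sample t test". It names no visit.

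On the variable, the Synopsis has immunogenicity "defined by antibodies serum titer (such as anti-MAGE-A3" and Section 2.1 "as measured by antibodies serum titers (such as anti-MAGE-A3) in patients with resected stage IV melanoma". Section 10.1.2 instead says that seropositivity status "will be the primary immune endpoints assessed. Seropositivity will be assessed at baseline, after 2, 4, 6, 7 and 9 administrations, post-treatment".

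**The concern.** The only power figure for the primary immune endpoint belongs to a visit with no scheduled blood draw. A reader of the final report could not say which titre comparison the 20 per arm were meant to support, or whether the primary immune result is a difference in mean log titre or a proportion seropositive.

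With seven post-baseline draws, no designated visit, and a statement in Section 10.4.3 that multiplicity will not be adjusted for, the most favourable visit could be put forward without contradicting the plan.

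A separate matter also affects the 62%. It assumes 20 measured patients per arm, but relapse stops treatment (Section 5.2.1.2) and missing titres are not replaced (Section 10.6.2). That would have lowered power at Visit 6 too, so it is not a consequence of the missing draw.

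**Working it through.** **1. Reproduce the stated power.** Inputs from Section 10.3: ratio 10,500/7,000 = 1.5, SD 0.28, 20 per arm, one-sided 0.05. The figure reproduces on the log10 scale, so the difference is log10(1.5) = 0.1761.

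Noncentrality = 0.1761 / (0.28 × √(2/20)) = 1.989, with 38 degrees of freedom and critical t 1.686. Power from the noncentral t is 0.621.

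| SD | 0.28 | 0.26 | 0.24 | 0.22 | 0.20 |
|---|---|---|---|---|---|
| Stated | 0.62 | 0.68 | 0.74 | 0.80 | 0.86 |
| Recomputed | 0.621 | 0.677 | 0.737 | 0.800 | 0.862 |

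The arithmetic is right.

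**2. Locate the powered measurement.** The first maintenance dose is dose 6, at Visit 6, month 6, week 24 (Table 6). Draws are at Visits 1, 3, 5, 7, 8, 10, 14 and F2, so 0 of 8 are at Visit 6. By dose count, a pre-dose Visit 6 sample would follow 5 doses; Sections 10.1.2 and 10.7.4 list 2, 4, 6, 7 and 9. The nearest draws are 12 weeks either side, against a 14-day window for maintenance visits. Table 6 is partly broken in the text available, but Table 8 and the prose confirm the gap independently.

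**3. What follows for power.** The documents give no geometric mean or SD at any sampled visit, so power there cannot be derived. The figures below are an illustration. They assume:

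- ratio 1.5 and SD 0.28 at every visit;
- exponential RFS with Section 10.3's medians of 12 and 24 months, so relapse-free fraction = 0.5^(months/median), in calendar months;
- every relapsed patient lost to the titre comparison;
- no other dropout or exclusion.

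Noncentrality = 0.1761 / (0.28 × √(1/n₁ + 1/n₂)), with n₁ + n₂ − 2 degrees of freedom. The n columns give ASCI alone / ASCI plus Poly IC:LC.

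| Visit | Relapse-free | n of 20 | Power | n of 22 | Power |
|---|---|---|---|---|---|
| V5, week 12 | 0.853 / 0.923 | 17.1 / 18.5 | 0.575 | 18.8 / 20.3 | 0.611 |
| V6, week 24 (not sampled) | 0.727 / 0.853 | 14.5 / 17.1 | 0.530 | 16.0 / 18.8 | 0.565 |
| V7, week 36 | 0.620 / 0.787 | 12.4 / 15.7 | 0.487 | 13.6 / 17.3 | 0.521 |

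With no relapse loss, power is 0.621 (20 per arm) and 0.658 (22 per arm). On like terms, moving from Visit 6 to Visit 5 gains about 5 points, and moving to Visit 7 loses about 4. The rest of the gap to 62% is relapse.

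Sensitivity with 22 per arm:

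| | V5 | V7 |
|---|---|---|
| Ratio 1.5, SD 0.36 to 0.20 | 0.442 to 0.854 | 0.372 to 0.767 |
| SD 0.28, ratio 1.3 to 2.0 | 0.346 to 0.951 | 0.292 to 0.895 |

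**4. No named visit.** One-sided 0.05 tests at all seven post-baseline draws would give a chance of at least one false positive of 1 − 0.95⁷ = 0.30 if independent. Simulation gives about 0.11 to 0.20 for assumed between-visit correlations of 0.9 to 0.5.

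**5. Titre versus seropositivity.** The 62% does not carry over to a proportion, and Section 10.3 plans only point estimates and 95% CIs for seropositivity. Section 1.2.3.3 reports an antibody response in every patient of the earlier metastatic melanoma trial, so seropositivity may sit near its ceiling in both arms. Under assumed rates, a one-sided Fisher test with 20 per arm has power 0.37 for 80% versus 100% and 0.04 for 90% versus 100%.

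**The case against.** The strongest objection is that the power illustration does not measure this flaw. It mostly models relapse, and it carries the month-6 ratio and SD to other visits without support. That stands, which is why the figures are illustrative only.

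It is also fair that losing every relapsed patient is close to a worst case at all three visits. A relapse found on a visit's own scan need not cost that visit's titre. If relapses surfaced only at scheduled scans, with Table 6 giving a routine scan at Visit 6 and one at Visit 7 only if indicated, the patients missing at Visit 7 would be those detected by Visit 6. Visit 7 power would then be the Visit 6 value, about 53% (20 per arm) or 56–57% (22 per arm).

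A second objection is phase II latitude. Titres are to be reported descriptively with confidence intervals, the absence of multiplicity adjustment is stated openly, and seropositivity is the same titre cut at a threshold. This softens the point without removing it: Section 10.3 makes the titre comparison the sole basis of the sample size, and no section presents Visit 5 or Visit 7 as a stand-in for month 6.

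Third, a change now cannot alter the design. Immunology collection ended on October 1, 2015, and this version is dated October 28, 2015. That is true, but Section 6.4.2 says analysis of existing samples continues, so the choice of visit and variable still matters.

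Finally, relapsed or withdrawn patients do give a humoral sample at the concluding visit (Section 6.3.9). That draw is triggered by an event and does not supply a Visit 6 comparison between arms.

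**Conclusion.** The concern holds and should be fixed. The powered measurement is at Visit 6, and every sampling schedule omits it. No sampled visit is designated primary, and two different variables are each called the primary immune endpoint. These conclusions rest on the documents alone.

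The 62% is not miscalculated; it describes a comparison that the scheduled samples cannot provide. Its value at a sampled visit is unknown. The illustrative range of 49% to 61% at Visits 5 and 7 depends on the assumptions listed and is near a worst case for relapse. The part attributable to changing the visit is only about +5 or −4 points, and only if ratio and SD are the same at each visit.

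**What to change.** Before titres are compared by arm, amend the text as follows; if titres have already been seen by arm, label the choices post hoc.

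- In Sections 10.3 and 10.7.4, name one sampled visit (Visit 5 or Visit 7) as the primary titre comparison, give the reason, and label the other visits descriptive.
- State whether mean log titre or seropositivity is the primary immune endpoint, and make Section 10.1.2 agree with the Synopsis, Section 2.1 and Section 10.3.
- In Section 10.3, say that the 62% was computed for a time point that is not sampled. Restate power for the named visit over a range of SDs above and below 0.28, ratios, and expected numbers measured.

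The cost is protocol and SAP wording. No sample or visit is added, since collection has ended, and the sample size does not change; the restated power tells the reader what the named comparison can show.
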